3.5.2. Medical intervention

The probability to reject the null hypothesis VE=0% for the endpoint medical intervention for a given one-sided significance level with 23 events is visualized in [Table 3](#). This probability is approximately 85% for an assumed VE=80% and approximately 99% for an assumed VE=90%. Therefore a minimum of 23 events is deemed sufficient to ensure a reasonable power for the evaluation of the medical intervention endpoint.

Table 3 Probability to reject the null hypothesis VE=0 for the endpoint medical intervention for a given one-sided significance level with 23 observed medical intervention endpoints

Available alpha	Information fraction	Probability for 80%VE	Probability for 90% VE
0.0065	20/154	85%	99%
0.00665	30/154	85%	99%
0.0069	50/154	85%	99%

0.0079	100/154	85%	99%
0.0125	154/154	85%	99%

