5.5.4.4. Medical intervention

Vaccine efficacy will be summarized with a 95% confidence interval (methods in Appendix 8)

When sufficient number of events are observed, an adjusted confidence interval will be calculated with the alpha-level α^* derived as detailed in section 2. To evaluate the hypothesis $H_0: VE \leq 0\%$, the lower-limit of the adjusted confidence interval will be compared to 0%, the hypothesis of protection on medical intervention endpoints will be rejected if the lower limit of the confidence interval is $> 0\%$.

For cases, the follow-up time is defined as the time between double-blind vaccination and the onset of the first event (according to the considered event linked to the medical intervention). For non-cases, it is the time between double-blind vaccination and data base cut off date (for subjects ongoing) or study discontinuation.

The reason linked to medical intervention will be tabulated.

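### Table 3 overstates the power for the medical-intervention endpoint at VE 80%: with 23 events the specified exact test gives 82.8%, not about 85%

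*SAP*

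**What the plan says.** SAP section 3.5.2 (Medical intervention) reports the power to reject VE=0% "for a given one-sided significance level with 23 events is visualized in" Table 3, and summarises it so: "This probability is approximately 85% for an assumed VE=80% and approximately 99% for an assumed VE=90" percent. Table 3 has five rows, running from "0.0065 20/154 85% 99" percent to "0.0125 154/154 85% 99" percent. The two power columns are the same in every row. The section then concludes: "Therefore a minimum of 23 events is deemed sufficient to ensure a reasonable power" for this endpoint. It does not name the test or formula behind the table.

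The test itself is set elsewhere. Section 5.5.4.4 says "When sufficient number of events are observed, an adjusted confidence interval will be calculated", and its lower limit is compared with 0%. That section refers to Appendix 8, which builds the interval from the exact binomial interval for the vaccine share of cases. Section 3 states that all sample size and power calculations date from protocol design and have not been updated.

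**The concern.** A power of 85% that stays constant while alpha nearly doubles is what a discrete exact test produces, because the same critical value can serve a range of alphas. That makes the figure easy to check. The VE 80% column does not come back from the exact test, whereas the VE 90% column does.

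Little is at stake. Medical intervention is a key confirmatory secondary endpoint, and section 3.5.2 is where the plan supplies and justifies an event count for testing it. That justification should quote the power the specified test has. The 23 is also worded as a minimum, so a reader may assume that the quoted power holds at 23 events or more.

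**Working it through.** **Inputs**
- Allocation 1:1 (section 3.1).
- Given n cases in total, vaccine cases X follow Binomial(n, π) with π = (1 − VE)/(2 − VE) (section 5.4.3.1; Appendix 8 with equal follow-up, r = 1).
- Null VE = 0%, so π₀ = 1/2.
- VE 80%: π₁ = 0.2/1.2 = 1/6. VE 90%: π₁ = 0.1/1.1 = 1/11.
- n = 23; one-sided alpha 0.0065, 0.00665, 0.0069, 0.0079 or 0.0125 (Table 3).
- Rejection when the exact lower limit for VE exceeds 0%. This is the same as X ≤ c, where c is the largest integer with P(X ≤ c | n, 1/2) ≤ alpha.

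**Step 1: critical value at 23 events**
- P(X ≤ 5 | 23, 1/2) = 44,552 / 8,388,608 = 0.0053
- P(X ≤ 6 | 23, 1/2) = 145,499 / 8,388,608 = 0.0173

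All five alphas lie between these two values, so c = 5 in every row. This accounts for the constant columns.

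**Step 2: the plan's figure at VE 90%**

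P(X ≤ 5 | 23, 1/11) = 0.985. The stated 99% is reproduced after rounding.

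**Step 3: the plan's figure at VE 80%**

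P(X ≤ 5 | 23, 1/6) = 0.0151 + 0.0694 + 0.1528 + 0.2139 + 0.2139 + 0.1625 = 0.8276.

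The stated 85% is not reproduced. The gap is 85 − 82.76 = 2.24 points, the same in every row.

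**Step 4: could another method give a constant 85%?**

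Over the five rows, the uncorrected normal approximation gives 83.1, 83.4, 83.8, 85.4 and 90.0%, and the arcsine approximation gives 84.5, 84.7, 85.0, 86.1 and 89.6%. Neither is constant, and neither is near 85% at alpha 0.0125. The exact calculation with π₁ cut from 0.1667 to 0.16 gives 85.02% in every row. That is a possible source, but nothing in the SAP confirms it.

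**Step 5: event counts around the stated minimum (VE 80%, exact test)**

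| Events | alpha 0.0065–0.0069 | alpha 0.0079 | alpha 0.0125 |
|---|---|---|---|
| 22 | 70.0% (c=4) | 70.0% (c=4) | 85.3% (c=5) |
| 23 | 82.8% (c=5) | 82.8% (c=5) | 82.8% (c=5) |
| 24 | 80.0% (c=5) | 80.0% (c=5) | 90.9% (c=6) |
| 25 | 77.2% (c=5) | 89.1% (c=6) | 89.1% (c=6) |
| 26 | 87.1% (c=6) | 87.1% (c=6) | 87.1% (c=6) |
| 27 | 85.0% (c=6) | 85.0% (c=6) | 93.2% (c=7) |
| 28 | 91.8% (c=7) | 91.8% (c=7) | 91.8% (c=7) |

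The dip at 25 events arises because P(X ≤ 6 | 25, 1/2) = 0.0073 exceeds 0.0069 but not 0.0079. Section 5.4.1 requires at least 42 primary events from Day 29 before efficacy monitoring starts. The 20/154 and 30/154 rows therefore cannot occur, but the 50/154 row (alpha 0.0069) can.

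**The case against.** The strongest reply is that this hardly matters. The text says approximately, the gap is 2.2 points, and the VE 90% column is right. The section claims only a reasonable power and sets no 85% requirement, and 82.8% meets that wording. The choice of 23 also has a sound basis: at 22 events power is 70.0% in four of the five rows, and 23 is where the critical value becomes 5 in all of them. The calculation dates from design and, per section 3, was not updated. Endpoints already tested at the primary analysis are now only summarised with 95% intervals (section 2). All of this stands, and it limits the point to a correction of a stated figure. It does not make 85% the power of the specified test.

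A reader might go further and infer that the plan promises 85% but may deliver 77%, or that the 23-event minimum is undermined. The document does not support this. Table 3 claims power only for 23 observed events. The 77.2% arises only at exactly 25 events with alpha below 0.0073, and the saw-tooth is a general property of exact tests. A reader might also take 22 events, with 85.3% at alpha 0.0125, as the origin of the figure. That cannot explain a column that reads 85% in all five rows, since 22 events gives 70.0% in the other four. The origin of the 85% is unknown.

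**Conclusion.** The VE 80% column of Table 3 and the matching sentence in section 3.5.2 are wrong as written: they should read about 83% (82.8%) instead of about 85%. The 99% at VE 90% (98.5%) is correct as rounded. This rests on 1:1 allocation, equal follow-up in the two arms, and the exact binomial test to which section 5.5.4.4 leads through Appendix 8. The constant columns in Table 3 are consistent with that test.

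The point is minor. The statement that 23 events gives reasonable power holds at 82.8%. The lower values at 24 and 25 events are useful context for a count worded as a minimum, but they do not contradict anything the SAP states.

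**What to change.** In section 3.5.2 and Table 3, change the VE 80% figure to about 83% in the text and in all five rows. State that the values come from the exact one-sided binomial test, with rejection at 5 or fewer vaccine cases out of 23. Leave the VE 90% column as it is.

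Optionally, since 23 is a minimum, add a footnote that exact-test power does not rise steadily with the event count. At VE 80% it is 80.0% at 24 events for alpha up to 0.0079, 77.2% at 25 events for alpha up to 0.0069, and about 85% or more from 26 events at every listed alpha.

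The cost is a text correction and a slightly lower stated power. No analysis, alpha level or decision rule is affected.

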3.5.3. Asymptomatic infections and all infections (including asymptomatic)

Based on assumptions prior to unblinding the cases in the placebo group were assumed to be distributed as follows: 45% asymptomatic cases and 55% symptomatic cases of which 20% were mild infections, and 60% were moderate and 20% were severe infections, according to the case definitions. Based on a VE as detailed in [Table 4](#), events were simulated according to a binomial distribution and the primary endpoints evaluated against the SPRT boundary.

Upon crossing the SPRT boundary, the power against asymptomatic or undetected infections as well as against the evaluation of all infections was calculated (null hypothesis $VE>0$). The alpha level for that evaluation was adjusted according to the procedure detailed in the statistical hypothesis evaluation.

The results are based on 1000 simulations. The powers presented are not conditional on passing the first 2 secondary hypotheses.

Table 4 Powers for Asymptomatic and All Infections for various Fractions of available N-Elisa samples at 2.5 months at the time of analysis

Fraction of available N-Elisa samples At 2.5 months	Vaccine efficacy			Power		
	Moderate/Severe	Mild	Asymptomatic	Moderate/Severe	Asymptomatic	All infections
100%	70%	60%	30%	99%	14%	96%
100%	70%	60%	40%	99%	28%	99%
100%	70%	60%	50%	99%	47%	>99%
50%	70%	60%	30%	99%	4%	99%
50%	70%	60%	40%	99%	7%	>99%
50%	70%	60%	50%	99%	13%	>99%

This is based on the protocol assumed incidence of 1.4% during 3 months and waning thereafter (by 50% in Month 4, by 62% in Month 5 and beyond) and a sample size of 60,000.

4. POPULATIONS (ANALYSIS SETS) FOR ANALYSIS

Vaccine assignment will be analyzed according to an as-treated principle. The analysis sets that are used for the various analyses are described in [Table 5](#).

Table 5 Analysis Sets

Analysis Sets	Description
Enrolled	The enrolled analysis set includes all participants who signed the ICF and who were not screen failures
Randomized	The randomized analysis set includes all participants who were randomized in the study.
Full Analysis Set (FAS)	All randomized participants with a documented study vaccine administration, regardless of the occurrence of protocol deviations and serostatus at enrollment.
Per Protocol Efficacy Set (PP; primary efficacy analysis set for vaccination studies)	Participants in the FAS who received double-blind study vaccine and who were seronegative at the time of double-blind vaccination and who have no major protocol deviations that were judged to possibly impact the efficacy of the vaccine. Participants who became aware of their study vaccine allocation will cease to be part of the PP population. See below for a definition.
Per Protocol Immunogenicity Analysis Set (PPI)	All randomized and vaccinated participants, including those who are part of the Immuno Subset and for whom immunogenicity data are available, excluding participants with major protocol deviations expected to impact the immunogenicity outcomes. In addition, for participants who experience a SARS-CoV-2 event (molecularly confirmed), samples taken after the event and samples taken outside protocol windows will not be taken into account in the assessment of the immunogenicity. The PPI population is the primary immunogenicity population. For key tables, sensitivity immunogenicity analyses will also be performed on the FAS, including participants who are part of the Immuno Subset for whom immunogenicity measures are available. Excluded samples might be taken into account as well in the sensitivity analysis. Analyses of vaccine immunogenicity and immune correlates of risk will be based on PPI.

For the PP the following additional criteria will be applied:

- having received the double-blind vaccine according to the randomization schedule
- having received at least 80% of the scheduled double-blind vaccination volume (according to the administration log)
- met inclusion criteria 1 (informed consent was obtained)

Some violations will not lead to exclusion of the subject from the PP, but data from the time-point of major protocol deviation onwards will be excluded as of from that moment from the analysis (if all data after double-blind vaccination is excluded, the participant will be excluded from the PP):

- use of prohibited concomitant medications or medical conditions that were judged to probably impact the efficacy of the vaccine based on blinded medical review will be assessed on a case by case basis and documented before confirming a case for continuous monitoring or data base lock
- administration of another SARS-CoV-2 vaccine before or during the trial

The following variables are relevant for in/exclusion of analyses:

- Seropositive or seronegative at baseline. A baseline serologic test for past or current infection with SARS-CoV-2 will be performed for all participants. Samples for the baseline serologic tests will be sent to the central lab for testing. Results will be categorized as positive or negative. If a participant is seropositive at baseline, the participant will be excluded from the PP set. In case the test result is missing or unknown the participant will be considered as seronegative for analysis purposes.
- PCR positive (PCR+) or negative (PCR-) at baseline: a sample for SARS-CoV-2 infection at baseline will be collected for each participant. For participants with a positive SARS-CoV-2 infection during the study this sample will be tested. If a participant was analyzed PCR+ at baseline, the participant will be excluded from the PP set. A missing value will be considered as PCR- for analysis purposes.

Timing of the infection: the onset of a symptomatic SARS-CoV-2 infection is defined in section [5.2](#). Based on the onset of infection, subjects will be included as

- For analysis with onset after double-blind vaccination: if onset occurred on or after Day 2 in the study (i.e. the Day after double-blind vaccination or beyond). At this stage there is however no expectation that the double-blind vaccination has achieved its full efficacy.
- For analysis with onset at least 14 days after double-blind vaccination: if onset occurred at or after Day 15. Subjects with an onset prior or at Day 14 will be excluded from the analysis.
- For analysis with onset at least 28 days after double-blind vaccination: if the onset occurred on Day 29 or beyond. Subjects with an onset prior or at Day 28 will be excluded from the analysis.

Analyses of safety will be performed on the FAS.

Analyses of efficacy will be performed on the PP population and will be repeated on the FAS.

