5.3. Participant Dispositions

Participant information will be shown for the full analysis set.

The number of participants in the following disposition categories will be summarized throughout the study by intervention group and overall:

- participants screened
- participants screen failed (and main reason for screen failure)
- participants in the FAS
- participants in the PP
- participants in the FAS but not in the PP (and reasons for not being in the PP)
- participants vaccinated and not randomized
- participants randomized and not vaccinated
- participants vaccinated with incorrect treatment
- participants who discontinued study (and reasons for termination)
- participants unblinded
- participants crossed over
- participants having another COVID-19 vaccine

Also, the number of participants and percentage per phase will be tabulated.

Graphical displays will be created for the follow-up time in the double blind phase for all subjects, by country, age, co-morbidities as well as by age crossed with co-morbidities will be visualized.

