5.4.7. Tabulations and Graphical displays

The time to onset of the first occurrence of molecularly confirmed COVID-19 (definition in section 5.2.4) will be graphically summarized using Kaplan-Meier methods for the following subgroups:

For moderate or severe/critical COVID-19,

- PP, seronegative subjects only with onset at least 14 days and at least 28 days after double-blind vaccination (co-primary endpoints)
- PP, seronegative subjects only with onset 1 day after double-blind vaccination
- PP, seronegative and seropositive subjects with onset 1 day after double-blind vaccination
- FAS, seronegative subjects only with onset 1 day after double-blind vaccination
- FAS, seronegative and seropositive subjects with onset 1 day after double-blind vaccination

*Note that in the PP there are no baseline-seropositive subjects – this population is defined as subjects who are baseline-seropositive and otherwise comply with the PP analysis set definition (e.g. no major protocol deviations).

These graphs will be summarized combined as well as for each type of infection separately (moderate or severe/critically ill COVID-19).

Furthermore, the number of events and incidence for each endpoint and population (#of events/#person-years of follow-up) will be tabulated by randomized group. For the tabulations regardless of serostatus, cases will be additionally summarized by serostatus at baseline and combined.

To assess potential time-effects of VE, two additional graphical explorations will be conducted. First, the Kaplan-Meier method will be used to plot the estimated cumulative incidence rates over time for the vaccine and placebo groups. This method will be used to estimate cumulative VE over time, defined as $[(1 \text{ minus ratio (vaccine/placebo)} \text{ of cumulative incidence by time } t) \times 100\%]$ with the method of Parzen, Wei and Ying applied to estimate pointwise and simultaneous $(1 - \alpha) \times 100\%$ CIs. Secondly, the method of Gilbert et al. (2002) will be used to evaluate VE over time based on the ratio of the smoothed instantaneous hazard in the vaccine and the placebo arm. More specifically, graphs will be created with $[(1 \text{ minus ratio (vaccine/placebo)} \text{ of smoothed instantaneous hazard by time } t) \times 100\%]$ and accompanying pointwise and simultaneous $(1 - \alpha) \times 100\%$ CIs over time since vaccination.

Any subgroup analysis for VE will also be visualized with forest plots.

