Safety analyses will be performed on the FAS. No formal statistical testing of safety data is planned. Safety data by double-blind vaccination group will be analyzed descriptively. Specific safety analyses will be performed on the Safety Subset. All safety analyses will be tabulated by treatment group (active vaccine, placebo) according to the as-treated principle. All safety analyses will be presented overall and by age and comorbidity (with/without) strata. The main age strata for reporting purposes are ≥ 18 to < 60 years of age and ≥ 60 years of age. In addition, safety data will be analyzed by treatment group and participant seropositivity status at screening.

For the double-blind phase, the safety data up to the unblinding date will be presented separately for the Ad26.Cov 2 double-blind group and the placebo double-blind group (Analysis I). Safety data after the unblinding date but before the open label vaccination date are listed separately.

Additionally, safety data will be pooled for all subjects that received Ad26.Cov 2 (in the double blind phase or in the open label phase) from the start of their Ad26.Cov 2 vaccination to the end of the trial (Analysis II): unsolicited AEs up to day 28, SAEs and MAAEs leading to discontinuation during the entire study, MAAEs until 6 months after last vaccination, AEs of special interest and AEs of interest during the entire study. All tables will be presented by phase.

The safety data from subjects that were unblinded and who received a vaccine outside the study will be tabulated separately.

Subjects that took another COVID-19 vaccine before being unblinded are excluded from the safety tables from the moment they received the other vaccine. The safety data from those subjects after they received the other vaccine are listed separately.

Denominator for the percentages is the number of participants in the considered population and phase for a certain regimen (incidence per 100 participants/phase).

Continuous variables will be summarized using the following statistics, as appropriate: number of observations, arithmetic mean (mean), 95% CI for the mean, standard deviation (SD), median, quartiles (Q1 and Q3), minimum and maximum. Frequencies and percentages (one decimal place) will be generated for categorical variables. No formal comparisons between groups will be provided.

Other exploratory or sensitivity analyses may be performed in addition to the analyses described below on an ad-hoc basis.

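### All safety analyses use a set that requires randomization, so anyone vaccinated without being randomized falls outside the vaccine-versus-placebo safety tables

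*SAP*

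**What the plan says.** **Who is in the set.** SAP Section 4, Table 5, defines the FAS as "All randomized participants with a documented study vaccine administration, regardless of the occurrence of protocol deviations and serostatus at enrollment". Section 5.9.1 confirms that both randomization and treatment are needed. Table 5 contains no safety set.

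**What the set is used for.** Section 4 states "Analyses of safety will be performed on the FAS" and also "Analyses of efficacy will be performed on the PP population and will be repeated on the FAS". Section 5.7 repeats that safety is analysed on the FAS, and both its opening list and Section 5.7.1.1 tie SAEs and AESIs to FAS participants. Section 5.7 adds a pooled analysis (Analysis II): "Additionally, safety data will be pooled for all subjects that received Ad26.Cov 2 (in the double blind phase or in the open label phase").

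**Who is foreseen.** Section 5.3 lists "participants vaccinated and not randomized" as a disposition category, and separately lists people vaccinated with the incorrect treatment. The same section says participant information is displayed for the FAS.

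**Which arm applies.** Section 4 gives one unrestricted rule: "Vaccine assignment will be analyzed according to an as-treated principle". Section 5.7 applies it to safety: "All safety analyses will be tabulated by treatment group (active vaccine, placebo) according to the as-treated principle". Section 5.9.1 says a participant not given the assigned treatment is counted as treated in the FAS and leaves the PP set. Section 5.4.7, however, says events and incidence for each endpoint and population "will be tabulated by randomized group". Section 5.5.1 says the same for secondary endpoints. Both sections list FAS populations. The severe-case harm test in Section 5.9.3 is also worded by the arm to which the participant was assigned.

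**The concern.** The purpose of an as-treated safety analysis is to follow exposure. A person who received the study injection without being randomized was exposed, but the membership rule keeps that person out of the set on which the two arms are compared for safety. For SAEs, deaths and rare AESIs, a few uncounted exposed people could matter. The SAP already provides for the category, so it should also say where those people's safety data go.

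The secondary issue is the arm label in the FAS. The FAS repeat of the efficacy analyses retains people whom the PP set drops, including those given the other arm's product. For these people the sections name opposite arms. If this is not settled in the plan, it will be settled by people who already know the treatment codes, because sponsor personnel were unblinded at the primary analysis (Section 1).

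**Working it through.** No figure in the plan is at issue on this point. The check is a side-by-side reading plus one illustration.

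**1. Safety membership.** Take a person vaccinated but not randomized and follow the text.

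| Output | Set or rule in the SAP | Included? |
|---|---|---|
| Disposition row (5.3) | Category listed, but the display is for the FAS | Contradictory: the FAS cannot contain this person |
| Double-blind comparison, Analysis I (5.7) | FAS, as treated | No |
| SAE, AESI and MAAE tables (5.7, 5.7.1.1) | FAS | No |
| Pooled analysis, Analysis II (5.7; phases in 5.1.2) | Recipients of Ad26.COV2.S, in a section that puts safety on the FAS | Unclear; never for a placebo-only recipient |
| Listings and/or narratives (5.7.1.2) | Deaths, SAEs and discontinuations due to an AE, as appropriate; no set named | Possibly, as individual records only |

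The as-treated rule does not help, because it decides the arm of someone already in the set, not who is in it.

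**2. Arm rule in the FAS.** Take a randomized person given the other arm's product.

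| Section | Arm |
|---|---|
| 4 | As treated |
| 5.9.1 | As treated in the FAS; excluded from PP |
| 5.4.7 and 5.5.1 (FAS populations listed) | As randomized |
| 5.9.3 (harm test on the FAS) | As assigned |

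In the PP set the rules agree, because Section 4 requires vaccination according to the randomization schedule. A person who received too small a volume also leaves the PP set but has the same arm under either rule. Only a wrong-product recipient changes arm.

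**3. Size of the arm effect.** Inputs: the SAP's design value of 60% vaccine efficacy (Section 3.1), hence relative risk 0.4; about 40,000 participants (Section 3.1); and a share m of each arm given the other arm's product. The SAP does not give m, so it is an assumption. Swaps are taken as unrelated to risk. As-treated analysis then gives 60%. As-randomized analysis gives

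VE = 1 − [(1 − m) × 0.4 + m] / [(1 − m) + 0.4 × m].

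- m = 0.01% (about 4 people): 1 − 0.40006/0.99994 = 59.99%
- m = 0.1% (about 40): 1 − 0.4006/0.9994 = 59.92%
- m = 0.5% (about 200): 1 − 0.403/0.997 = 59.58%
- m = 1% (about 400): 1 − 0.406/0.994 = 59.15%

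**4. Size of the safety gap.** The SAP gives no number of people vaccinated without randomization and no rate from which to derive one, so no figure can be put on this part.

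**The case against.** There is a fair case that little is wrong. Randomization is central, so the vaccinated-not-randomized row may simply read zero; listing a category does not show that it is expected to be filled. That stands, and it is why no count is attached to the gap.

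A reader might infer that an event in such a person would appear in no safety output at all. The documents do not support that. Analysis II is worded by receipt of Ad26.COV2.S, and the listings and narratives name no analysis set. Neither closes the gap, however. Section 5.7 itself puts safety on the FAS, Analysis II leaves out placebo-only recipients, and narratives supply no numerators or denominators for the comparison between arms.

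A reader might also infer that the FAS is the wrong set for both of its uses. That goes too far. As-treated allocation is sound for safety, where only membership is at fault. A randomized-and-vaccinated set is a usual choice for supportive efficacy, where only the arm label is in doubt.

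On that label, Section 5.9.1 speaks directly to the wrong-product case, and the randomized-group wording may be no more than a generic name for the arms. This is plausible, and it makes the efficacy point minor. It remains a contradiction, because Sections 5.4.7 and 5.5.1 say what they say for every population listed.

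**Conclusion.** The point holds for safety. Following the SAP as written leaves anyone vaccinated without randomization out of the vaccine-versus-placebo safety tables, and their place in the pooled analysis and narratives is undetermined. The size is unknown and may be zero. The case for acting is that every exposure should be accounted for by rule.

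The efficacy part is real but small. The FAS arm rule is stated in two ways, and only wrong-product recipients are affected. At the assumed swap rate of 0.1% per arm the difference is under 0.1 percentage point of vaccine efficacy, and at 1% it is about 0.85 point (60 − 59.15). These figures assume a true efficacy of 60%, equal swap rates in both arms and swaps unrelated to risk. It would be wrong to conclude that the co-primary or confirmatory results are in question: those tests use the PP set, where treated and randomized arms coincide. The harm monitoring ended when the primary analysis was triggered, so for Section 5.9.3 this is now a matter of consistent wording.

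**What to change.** **Safety.** Add to Table 5 a Safety Set: all participants with a documented study vaccine administration, whether or not randomized, analysed as treated. Name it in place of the FAS for safety in Sections 4 and 5.7, including 5.7.1.1, and say that Analysis II draws on it. In Section 5.3, show the vaccinated-not-randomized row outside the FAS. The cost is wording and one population flag. The downside is that safety denominators may differ from the FAS by a few participants; if the row is zero, the sets are the same.

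**Arm rule.** Reconcile Sections 4, 5.4.7, 5.5.1, 5.9.1 and 5.9.3 to one stated rule for efficacy on the FAS. Because sponsor personnel are already unblinded, keep whichever rule the primary analysis used, so that the results stay comparable and no new choice is made with codes known. If that rule was as treated, add the as-randomized FAS result as a sensitivity analysis and correct the table wording in Sections 5.4.7 and 5.5.1. If it was as randomized, limit the as-treated sentence in Section 4 so that it does not cover FAS efficacy, and amend Section 5.9.1. The cost is confirming what was done at the primary analysis and, in the first case, one additional run of the FAS efficacy tables.
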